8.8.2 Suspicion of acute gallstone disease

In case of suspicion of acute gallstone disease or cholelithiasis, the trial product must promptly be discontinued (no 'treatment status' session should be made in IWRS before a diagnosis of acute gallstone disease is confirmed). Appropriate treatment and careful monitoring should be initiated. Furthermore, the subject should remain in the trial (see Section [8.1](#))

The event must be reported as an AE requiring additional data collection (see Section [8.4.3.2](#) and Section [12](#)).

If acute gallstone disease is confirmed, the trial product must be permanently discontinued. However, trial product can be restarted at the investigator's discretion if cholelithiasis is ruled out or the gallbladder has been removed. Appropriate treatment and careful monitoring of the subject should be initiated. Furthermore, the subject should be encouraged to remain in the trial (see Section [8.1](#)).

8.8.3 Neoplasm

In case of neoplasm, please consider if the trial drug should be discontinued (no 'treatment status' session should be made in IWRS before a diagnosis is confirmed). The event must be reported as an AE requiring additional data collection (see Section [8.4.3.2](#) and Section [12](#)). Appropriate treatment and careful monitoring of the subject should be initiated. Furthermore, the subject should be encouraged to remain in the trial (see Section [8.1](#)).

Trial product can be re-initiated at the investigator's discretion if diagnosis is not supported.

8.8.4 Hepatic event (suspicion of drug-induced liver injury)

Please consider discontinuing trial product if :

- 1) ALT or AST >5xUNL, or

2) ALT or AST > 3x UNL and (total bilirubin >2xUNL or INR >1.5), or

3) ALT or AST >3xUNL with the appearance of fatigue, nausea, vomiting, right upper quadrant pain or tenderness, fever, rash, and/or eosinophilia (>5%).

For the above events, prompt repeat testing at central laboratory, of ALT, AST, ALP, INR and total bilirubin should be done. Thereafter, repeat testing (at central laboratory) of ALT, AST, ALP, INR and total bilirubin should be done regularly until the abnormalities return to normal or baseline state. Additional clinical information such as related symptoms, risk factors and contributing conditions (e.g. viral hepatitis, autoimmune hepatitis, alcoholic hepatitis, hepatobiliary or pancreatic disorders) should be gathered to seek a possible cause of the observed laboratory test abnormalities. Although the trial product is discontinued, no 'treatment status' session should be made in IWRS and the subject should remain in the trial.

In case of suspicion of DILI, the trial product must promptly be discontinued (no 'treatment status' session should be made in IWRS before a diagnosis is confirmed).

The event must be reported as an AE requiring additional data collection (see Section [8.4.3.2](#) and Section [12](#)).

If DILI is confirmed, the subject should permanently discontinue the trial product. Appropriate treatment and careful monitoring of the subject should be initiated. Furthermore, the subject should be encouraged to remain in the trial (see Section [8.1](#)).

Trial product can be re-initiated at the investigator's discretion if diagnosis of DILI is not supported.

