5.3 Treatment of subjects

5.3.1 Investigational medicinal product

The investigational medicinal product (IMP) is injected subcutaneously (s.c.) once daily for 56 weeks. Dose escalation of trial product will take place during the first 4 weeks after randomisation (see [Table 5-1](#)).

Table 5-1 Dose escalation and treatment period

IMP	Dose	Duration
Liraglutide/placebo	0.6 mg	1 week
Liraglutide/placebo	1.2 mg	1 week
Liraglutide/placebo	1.8 mg	1 week
Liraglutide/placebo	2.4 mg	1 week
Liraglutide/placebo	3.0 mg	52 weeks
Follow up period	0 mg	4 weeks

If the subject does not tolerate an increased dose during the dose escalation window, the investigator can delay the dose escalation by maintaining the subject at the current dosage step for one additional week. Such a delay is allowed only once during dose escalation (i.e. maximum allowed time for complete dose escalation to 3.0 mg is 5 weeks). After reaching the maintenance dose (3.0 mg), the dose and dosing frequency should not be changed.

If a single dose is missed, the once-daily regimen should be resumed as prescribed at the next scheduled dose. If more than 3 consecutive days have elapsed since the last dose, subject should re-initiate dose escalation, (e.g. restart the dosing at 0.6 mg and follow the dose escalation schedule again). This is done to reduce the occurrence of gastrointestinal symptoms associated with re-initiation of treatment.

NB: Additional or increased dose should not be taken to make up for missed doses.

Trial product can be taken at any time of day, irrespective of timing of meals. Trial product can be injected s.c. in the abdomen, thigh, or upper arm. The injection site and timing can be changed without dose adjustment.

NB: Trial product must not be administered intravenously or intramuscularly.

If a subject cannot tolerate the 3.0 mg dose, or if any of the other treatment discontinuation criteria are met, then treatment with trial product must be discontinued. For treatment discontinuation reasons, please refer to Section [6.5](#). In case this happens, it is acceptable to restart trial product (at the discretion of investigator and according to the local clinical practice); the dose must be escalated according to the algorithm above, and date of restart and rationale must be documented in the CRF.

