6.5 Criteria for premature discontinuation of trial product

Efforts must be made so that subjects attend and complete all scheduled visit procedures. Subjects should stay in the trial regardless of adherence to randomised treatment, adherence to visit schedule or missing assessments. Only subjects who decline any further contact with the site in relation to the trial or withdraw consent are considered as withdrawn from the trial (see Section [6.6](#)).

The subject may be prematurely discontinued from trial product at the discretion of the investigator due to a safety concern.

The subject must be prematurely discontinued from trial product if the following applies:

1. Included in the trial in violation of any of the inclusion and/or exclusion criteria and/or randomisation criterion
2. Safety concern (not covered by any of below criteria) or unacceptable intolerability to trial product, as judged by the investigator
3. Hypersensitivity to trial product(s). If a hypersensitivity reaction occurs, discontinue trial product and other suspect medications
4. More than one episode of severe hypoglycaemia, or repeated episodes of documented symptomatic hypoglycaemia (ADA classification), despite lowering of insulin dose (as judged by investigator)
5. Pregnancy
6. Intention of becoming pregnant
7. Suspicion of pancreatitis (see Section [8.4.3.2](#) and [8.8.1](#))
8. Suspicion of acute gallstone disease (see Section [8.4.3.2](#) and [8.8.2](#))
9. Suspicion of drug-induced liver injury (DILI) (see Section [8.4.3.2](#) and [8.8.4](#))
10. Calcitonin ≥ 100 ng/L
11. Psychiatric disorder(s) that cannot be adequately treated with psycho- and/or pharmacotherapy (see Section [8.4.3.2](#), [8.6.5](#) and [8.8.5](#))
12. Initiation of anti-obesity medication and/or (plans for) weight loss surgery
13. Initiation of treatment with GLP-1 receptor agonist or DPP-IV inhibitors

14. Simultaneous participation in another clinical trial of an approved or non-approved investigational medicinal product

See Section [8.1](#) for procedures to be performed for subjects discontinuing trial product prematurely.

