It is allowed for subjects meeting the premature discontinuation criteria or who have wished to discontinue prematurely to be restarted on the trial product should the suspicion not be confirmed or if the condition has been resolved at the investigator's discretion. Trial product may be restarted for subjects meeting discontinuation criteria 8 should the gallbladder be removed.

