If a subject meets a discontinuation criterion, the trial product must be immediately discontinued and the date should be noted in the medical records and eCRF. Discontinuation can be either temporary or permanent. The last paragraph of Section [6.5](#) outlines which discontinuation can be considered temporary. The investigator must also note down the date in the medical record and eCRF once there is resolution and the subject has re-started the trial product.

The subject may also wish to discontinue trial product temporarily or permanently, irrespective meeting any criteria. Discontinuation of treatment with trial product, whether temporary or permanent, must not prompt the investigator to withdraw the subject from the trial. Instead, the subject should maintain adherence to trial visits and procedures to the extent possible.

In cases where the subject is not willing to attend all scheduled visits after discontinuation of trial product, efforts must be made to collect as much of the scheduled data as possible. Especially important is collection of the data points (primarily) at visit 24 (week 56). Statistical considerations emphasizing the importance can be found in Section [17](#).

Premature trial product discontinuation should be registered in the eCRF and in IWRS. The trial product can be interrupted by performing a 'treatment status' session in IWRS, to indicate subject should no longer receive trial product. The primary reason for discontinuation of trial product must be specified when recording the treatment discontinuation in the eCRF. If the discontinuation of trial product is judged permanent or of a longer period, drug accountability until discontinuation must be performed in IWRS.

If the subject has previously discontinued trial product, it is possible, at the discretion of the investigator and at the wish of the subject, to re-initiate treatment with trial product. This will only apply if it can be confirmed that the subject has not withdrawn consent, does not fulfil any of the criteria, leading to permanent discontinuation or if a criterion leading to temporary discontinuation has been resolved. A 'treatment status' session is performed in the IWRS, to indicate that the subject should again receive trial product. See Section [10](#) for registration in IWRS. This should be further noted in the medical records and eCRF.

Withdrawal from trial

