In case of suspicion of drug-induced liver injury (DILI), following additional information should be reported if available on the drug induced liver injury form:

- Signs and symptoms of drug induced liver injury
- Specific laboratory test supporting a diagnosis of drug induced liver injury (see Section [8.8.4](#))
- Treatment given for the event
- Relevant risk factors associated with the event

Prompt testing (at central laboratory) including alanine aminotransaminase (ALT), aspartate aminotransferase (AST), alkaline phosphatase (ALP), international normalised ratio (INR) and total bilirubin (TBL) should be done and trial product should be discontinued until the abnormalities return to normal or baseline state.

Additional clinical information such as related symptoms, risk factors and contributing conditions (e.g., viral hepatitis, autoimmune hepatitis, alcoholic hepatitis, hepatobiliary or pancreatic disorders) should be gathered to seek a possible cause of the observed laboratory test abnormalities.

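### On suspected drug-induced liver injury, Protocol 8.4.3.2 holds trial product until liver tests recover, but the restart rules in 8.8.4 and 6.5 allow earlier re-exposure

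*Protocol*

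**What the plan says.** Four places in the Protocol bear on this.

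- **8.4.3.2, hepatic event.** On suspicion of DILI, prompt central testing of ALT, AST, ALP, INR and total bilirubin is called for, and "trial product should be discontinued until the abnormalities return to normal or baseline state".
- **8.8.4.** On suspicion, trial product must be stopped promptly. If DILI is confirmed, the stop is permanent. If not, trial product can be re-initiated at the investigator's "discretion if diagnosis of DILI is not supported". For subjects meeting one of its three enzyme-based criteria, repeat testing "should be done regularly until the abnormalities return to normal or baseline state".
- **6.5.** Criterion 9 makes suspicion of DILI a reason for mandatory discontinuation and refers to both 8.4.3.2 and 8.8.4. The closing paragraph allows restart, at the investigator's discretion, "should the suspicion not be confirmed or if the condition has been resolved".
- **12.1.5.** This lists the events that need specific forms, cites 8.4.3.2 for the forms, and sends the reader to Section 8.8 for the details of the events.

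The changes listed in Amendments 1 to 3 do not touch 6.5, 8.4.3.2, 8.8.4 or 12.1.5.

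**The concern.** The same trigger, suspicion of DILI, leads to two different rules for ending the hold. The rule in 8.4.3.2 is a laboratory one: the abnormalities must have gone. The rule in 8.8.4 and in the first route of 6.5 is diagnostic: the suspicion must not have been borne out. A diagnosis can be set aside well before liver tests recover, so the rules can give different dates.

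What is at stake is whether a subject with liver tests still abnormal is put back on trial product. In a multi-national trial, sites reading in good faith could decide this differently, and a monitor would have no clear standard for calling an early restart a deviation.

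**Working it through.** No arithmetic applies. The check is to set the provisions side by side and run one case through them.

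| Section | Scope | What ends the hold | Laboratory condition? |
|---|---|---|---|
| 8.4.3.2 | Suspected DILI | Abnormalities back to normal or baseline | Yes |
| 8.8.4 | Suspected DILI | DILI not supported, investigator's discretion | No |
| 6.5, first route | Any suspicion-based criterion, including 9 | Suspicion not confirmed, investigator's discretion | No |
| 6.5, second route | Any criterion | Condition resolved, investigator's discretion | Not stated; could be read in |

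**Step 1: does the laboratory end point in 8.8.4 reach restart?** No. Recovery of the tests appears there only as the point at which repeat testing may stop. The restart sentence does not refer to it.

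**Step 2: does the second route in 6.5 close the gap?** No. One could read resolution of the condition as recovery of the tests, but the two routes are joined by *or*, so the first is enough by itself.

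**Step 3: a test case.** ALT rises above five times the upper normal limit and DILI is suspected. The rise is then put down to viral hepatitis, one of the contributing conditions that 8.8.4 itself lists, while ALT is still raised.

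- Under 8.4.3.2, trial product should stay off until ALT is normal or at baseline.
- Under 8.8.4 and the first route of 6.5, the investigator may restart now.

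**Step 4: does the clause in 8.4.3.2 do any work if 8.8.4 alone governs?** Almost none. A confirmed case is off drug permanently, and a case under evaluation is already off drug. The clause can set a restart date only where DILI is not confirmed, which is where 8.8.4 leaves it out.

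**Step 5: how far does this spread?** Section 8.4.3.2 covers five event types: gallstone disease, neoplasm, pancreatitis, depression or suicidality, and the hepatic event. Only the hepatic event (1 of 5) carries a drug-hold rule in that section, so the inconsistency stays with the liver.

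**Step 6: does it reach the primary analysis?** No. The effectiveness estimand uses week 56 weight regardless of adherence, and the primary imputation treats missing on-treatment and missing drop-out values alike (SAP 2.3.2.2). The restart date does not enter.

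**The case against.** The strongest reply is that nothing is contradicted. Section 8.4.3.2 recommends a hold, while 8.8.4 and 6.5 grant permissions. A site that waits until DILI is not supported and the tests have recovered complies with every section. This is right, and it rules out a reading that a reader might infer: that the Protocol gives orders that cannot all be obeyed. What stands is narrower. Two sections permit a restart earlier than the third advises, and none says that the conditions add up. Section 8.8.4 cites 8.4.3.2 only for event reporting and data collection.

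A second reply is that 12.1.5 settles the matter by sending readers to Section 8.8. It is not worded as a rule of precedence. Its practical effect is to make it likelier that a site follows the weaker rule.

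A third is that if 8.8.4 governs, the natural repair is to delete the clause in 8.4.3.2. Deletion would remove the inconsistency, but by dropping the only laboratory safeguard on restart.

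Two other stronger readings also fail. A reader might count the silence of the general restart permissions, in 5.3.1 ("it is acceptable to restart trial product (at the discretion of investigator and according to the local clinical practice") and 8.1 ("if a criterion leading to temporary discontinuation has been resolved"), as further evidence. Those rules cover every kind of discontinuation and would not be expected to carry a liver condition, so their silence adds little. A reader might also infer that all five named tests must be normal before restart. Section 8.4.3.2 speaks only of the abnormalities, and INR is not in the scheduled laboratory lists of 8.5.2, even as amended, so those lists supply no baseline INR.

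**Conclusion.** The point holds as a minor inconsistency in safety conduct. On suspicion of DILI, 8.8.4 and the first route of 6.5 permit re-exposure before the recovery of liver tests that 8.4.3.2 asks for.

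It rests on the plain wording of the sections and on there being no statement elsewhere in the documents supplied that the conditions are cumulative. The number of subjects affected is not given; it is limited to those in whom DILI is suspected, then judged not supported, while tests are still abnormal.

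It should not be read as allowing restart after confirmed DILI: 8.8.4 makes that stop permanent. Nor is restart ever automatic, since the investigator's judgement is always required. There is no effect on sample size, type I error or the primary analysis.

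**What to change.** Two wording changes and a note to sites:

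- **8.8.4, last sentence.** Allow re-initiation at the investigator's discretion only if DILI is not supported *and* the liver test abnormalities that led to the hold are back to normal or baseline. Tie it to those abnormalities, not to all five named tests.
- **6.5, restart paragraph.** Add: *For criterion 9 the condition in 8.8.4 applies.* The paragraph already has a clause of this kind for gallstone disease: "Trial product may be restarted for subjects meeting discontinuation criteria 8 should the gallbladder be removed".

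No change to 5.3.1 or 8.1 is needed.

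The cost falls on a few subjects. Those with another cause for their abnormal tests restart later, or not at all if the tests never recover. Subjects who meet an 8.8.4 threshold are already retested to normal or baseline, so they need no extra tests; those suspected below the thresholds would need repeat liver tests before restart. Scheduled visits, sample size and analysis are unchanged.

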8.8.5 Depression, suicidal ideation/behaviour

In case of depression or suicidal ideation/behaviour, please consider if the trial drug should be discontinued (no 'treatment status' session should be made in IWRS before a diagnosis is confirmed). The event must be reported as an AE requiring additional data collection (see Section [8.4.3.2](#) and Section [12](#)).

Appropriate treatment and careful monitoring of the subject should be initiated as per local clinical practice. A subject should be referred to a MHP if he/she has:

1. symptoms of moderate or more severe depression,
2. or any suicidal behaviour,
3. or any suicidal thoughts with some intent to act, irrespective of whether accompanied by a specific plan.

Protocol
Trial ID: NN8022-4272
UTN: U1111-1177-4903
EudraCT no.: 2015-005619-33

~~CONFIDENTIAL~~

Date:	14 September 2016	Novo Nordisk
Version:	4.0	
Status:	Final	
Page:	64 of 123	

In case the subject refuses to consult the MHP, the investigator must state in the medical records whether it is considered safe for the subject to stay in the trial. Trial product can be re-initiated at the investigator's discretion, if a diagnosis is not supported.

9 Trial supplies

Trial supplies comprise trial products and auxiliary supplies. Additional details regarding trial supplies can be found in the trial materials manual (TMM).

Trial products must not be dispensed to any person not included in the trial.

Trial product comprises investigational medicinal products (IMP); both active and placebo.

Trial product must not be used, if it does not appear clear and colourless or almost colourless.

9.1 Trial products

The following trial products will be provided by Novo Nordisk A/S, Denmark:

Table 9–1 Trial products

Trial product	Strength	Dosage form	Route of administration	Container/delivery device
Liraglutide 6 mg/mL (IMP)	6 mg/mL	Solution for injection	Subcutaneous injection (s.c.)	3 mL PDS290 pen-injector
Placebo (IMP)	NA			

Basal and bolus insulin and OADs are considered non-investigational medicinal products (NIMPs), hence will not be provided by Novo Nordisk. However, insulins and OADs will be reimbursed if required by the country's regulatory authority or IRB/IEC.

Liraglutide and placebo are visually identical, to ensure double-blinding in the trial.

9.2 Labelling and directions for use

The trial products will be labelled in accordance with Annex 13⁴², local regulations and trial requirements.

Each trial site will be supplied with sufficient trial products for the trial on an on-going basis controlled by the IWRS. Trial product will be distributed to the trial sites according to enrolment and randomisation.

The investigator must document that direction for use is given to the subject orally and in writing at the first dispensing visit (visit 2). At the following visits, the investigator will confirm with the

subject that the direction for use is still available and that the subject is using the trial product correctly.

9.3 Storage

Table 9–2 Storage conditions

Trial product	Storage conditions (not-in-use)	In-use conditions	In-use time ^a
Liraglutide 6 mg/mL		Store below 30°C Do not freeze Protect from light	
Placebo	Store in a refrigerator (2°C-8°C/ 36°F-46°F) Do not freeze Protect from light	US: Store at room temperature (59°F-86°F) or in refrigerator (36°F-46°F) Canada: 30 days at room temperature (not above 30°) or in a refrigerator (2°C-8°C)	Use within 1 month US: Use within 30 days

^a In-use time starts when the product is taken out of the subject's refrigerator

The investigator must ensure that trial product is kept under proper storage conditions and record and evaluate the temperature. The investigator must inform Novo Nordisk **immediately** if any trial product has been stored outside specified conditions (e.g., outside temperature range). Additional details regarding handling of temperature deviations can be found in the TMM.

Trial product that has been stored improperly must not be dispensed to any subject before it has been evaluated and approved for further use by Novo Nordisk. The investigator must take appropriate action to ensure correct storage.

9.4 Drug accountability and destruction

Drug accountability of all trial products received at site is the responsibility of the investigator.

The trial products will be dispensed to each subject as required according to treatment group. The IWRS will allocate trial product to the subject at randomisation and each dispensing visit. The correct dispensing unit number(s) (DUN[s]) must be dispensed to the subject.

The investigator or delegated person is responsible for ensuring that:

- Drug accountability is performed using the IWRS drug accountability module
- Subjects are instructed to return all used, partly used and unused trial product including empty packaging material at each dispensing visit and at end-of-treatment visit

Returned trial product (used/partly used and/or unused), expired or damaged trial product can be stored at room temperature and must be stored separately from non-allocated trial product.

Non-allocated trial products including expired or damaged products must be accounted as unused at the latest at closure of the trial site.

Dispensed trial product must be accounted for at pen level; either recorded as used/partly used, unused or lost. Distributed and returned pens are subject to be sent for destruction, thus may not be re-allocated to new subjects.

Destruction of trial products can be performed on an on-going basis and will be done according to local procedures after accountability is finalised and reconciled by the monitor. Destruction of products must be documented in the IWRS.

